4.1 Sample Size Calculations and recruitment schedule

The aim is to recruit 20 patients over a 24 month period. A Simon two stage minimax design to distinguish a <5% from a >25% improvement in the Mayo classification requires 20 evaluable patients (90% power, 10% 1-sided).

Thirteen patients would be recruited in the first stage. If no patients demonstrate an improvement in their Mayo classification between screening and week 9, accrual to the clinical trial would stop (see [Section 3.1.2](#)). If one or more patients demonstrate an improvement in the Mayo classification between screening and week 9, a further seven patients would be recruited (to the final total of 20 evaluable patients). In order for the clinical trial to be considered a success, at least three evaluable patients should demonstrate an improvement in disease or treatment between screening and week 9 (see [Section 7.6.1](#)).

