**Mayo Classification:**

- Level 0: thrombus limited to the renal vein
- Level 1: into IVC <2cm from renal vein ostium level
- Level 2: IVC extension >2cm from renal vein ostium and below hepatic vein
- Level 3: thrombus at the level of or above the hepatic veins but below the diaphragm
- Level 4: thrombus extending above the diaphragm.

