### **Primary Safety Endpoints**

Thirteen patients will be recruited at first; if at least 1 patient has an improvement in the Mayo classification a further 7 patients would be recruited (to the final total of 20 patients who have received study drug), to receive study drug. At least 3 patients showing reductions in Mayo score are required for a positive trial. The early stopping rules are:

- (1) If a single M0 patient progresses to the point where surgery is no longer possible, then recruitment of new patients will be suspended following a review by the data monitoring committee (DMC).
- (2) If a single M0 patient becomes M1 recruitment of new patients will be suspended following a review by the DMC.
- (3) If in 3 patients the VTT extends but patients remain surgically resectable the trial will close. If the VTT has extended the patient will be expedited and operated on as soon as possible.

Where there is diagnostic doubt at site, the week 3 MRI abdomen scans (and CT chest for M0 patients) a central review will be conducted to determine if a patient has progressed as per RECIST 1.1 criteria. In addition those particular patient cases will be discussed on an individual basis by the trial steering committee (TSC).

The central review for final analysis will be conducted by radiologists based at Addenbrooke's Hospital.

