### **9.2. Analysis Plan**

The main analysis will be conducted on the “as-treated” population. All patients who receive study drug will be included in the interim and final analysis. Any patient who withdraws from the study prior to receiving drug will not be included in the analysis. At least 3 patients showing a reduction in Mayo Classification would produce a positive trial.

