#### **Interim Analysis**

An interim analysis will be performed after thirteen patients have been recruited. If no patients have show an improvement in their Mayo classification the trial will be stopped for futility. If at any point in the study 3 patients have a progression of their thrombus (increase in Mayo classification) but remain surgically resectable the trial will be stopped. (Probability of seeing 3 or more progressions if true progression rate <5% is <7.5%). There is no formal stopping rule for efficacy.

The primary analysis will be made on the “treated” population, with patients being included in the analysis only if they have received at least one dose of the drug. In order to assess the impact of any biases an analysis of the “intention to treat” population will also be carried out.

This will include all patients who are registered as eligible for the trial, regardless of whether or not the subsequently received study medication.

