5.2 Early stopping rules

Patient safety will be ensured by applying the following early stopping rules:

- (1) If a single M0 (staging data: cancer has not spread to other parts of the body) patient progresses to the point where surgery is no longer possible, then recruitment of new patients will be suspended following a review by the data monitoring committee (DMC)
- (2) If a single M0 (staging data: cancer has not spread to other parts of the body) patient becomes a M1 (staging data: cancer has spread to other parts of the body) patient, recruitment of new patients will be suspended following a review by the DMC.
- (3) If in 3 patients the VTT extends (as indicated by an increase in Mayo classification) but patients remain surgically resectable the trial will close. If the VTT has extended the patient will be expedited and operated on as soon as possible.

6 Efficacy evaluations

Note that these evaluations will be made for both the evaluable and ITT populations. This represents a sensitivity analysis that assesses whether results are robust in the ITT population.

This study will use the following efficacy parameters:

- At least 3 evaluable patients showing improvement in disease extent between screening and week 9 are required for a positive trial.
- The change in Mayo classification between screening and week 9 in evaluable patients will be presented with the percentage of patients with an improvement, no change and a deterioration in Mayo classification shown. Percentages will be calculated using both the evaluable population and the ITT population.
- The VTT length measurement will be calculated as the sum of: (1) length of IVC tumour thrombus ABOVE renal vein (measured from ostium of RV+IVC to tip of tumour thrombus); (2) length of IVC tumour thrombus BELOW renal vein (measured from ostium of RV+IVC to tip of tumour thrombus) and (3) length of RV thrombus. Those patients who are identified as “main renal vein” will only have the third value populated. Any values that are missing cannot be assumed to represent 0 and must be clarified either via contact with sites or by manual checking of the paper CRF.

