6.1 Additional definitions

Definitions of the Mayo classification and surgical approach classification systems that should be used to define improvement are shown below:

Mayo classification (levels are ordered by increasing extensiveness):

- Level 0: thrombus limited to the renal vein
- Level 1: into IVC <2cm from renal vein ostium level
- Level 2: IVC extension >2cm from renal vein ostium and below hepatic vein
- Level 3: thrombus at the level of or above the hepatic veins but below the diaphragm
- Level 4: thrombus extending above the diaphragm.

Tumour thrombus surgical management approach classification (approaches are ordered by increasing invasiveness):

1. Thrombus - Milked back into renal vein and side clamped
2. Infra-hepatic (IVC clamping with no liver mobilisation)
3. Retro-hepatic (liver mobilisation and clamping below hepatic veins)
4. Retro-hepatic (liver mobilisation and clamping above hepatic veins)
5. Supra-hepatic (infradiaphragmatic)

6. Supra-hepatic (supradiaphragmatic)

Note that efficacy outcomes can be expressed as a percentage of the ITT population or the evaluable population (meaning that the denominator should change to be either the size of the relevant population).

7 Tabulations, Figures and Listings

This section is the complete operational specification for the statistical analysis and subsequent presentation of that analysis for the lifetime of this trial. Throughout this section, tabulations consist of counts and percentages per category unless stated otherwise. Listings will include the patient identifier and the specific data for that listing.

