7.6.1 Primary endpoints

NB. For all primary endpoint assessments, if a patient does not have a week 9 scan, then their week 3 scan (if available) should be used instead.

7.6.1.1 For patients presenting at screening with a Mayo Classification of Level 1 or above

- The number and percentage of patients with an improvement in the Mayo Classification between screening and week 9 (see [Section 6.1](#) for Mayo classification system).
- The number and percentage of patients with no change in the Mayo Classification between screening and week 9 (see [Section 6.1](#) for Mayo classification system).
- The number and percentage of patients with deterioration in the Mayo Classification between screening and week 9 (see [Section 6.1](#) for Mayo classification system).

7.6.1.2 For patients presenting at screening with a Mayo Classification of Level 0

- The number and percentage of patients demonstrating improvement in status, i.e.:

- For patients presenting with right renal vein tumour thrombus: a change of tumour thrombus from main renal vein to branches of the renal vein between screening and week 9.
- For patients presenting with left renal vein tumour thrombus: a change of tumour thrombus from the main renal vein between screening and week 9 as follows:
 - If the patient is lateral to the gonadal vein at screening, a change from the main renal vein into the segmental veins
 - If the patient is medial to the gonadal vein at screening, a change from the main renal vein medial to the gonadal vein to the renal vein lateral to the gonadal vein
- The number and percentage of patients with no change in tumour thrombus status (i.e., tumour still present in the main renal vein and medial to the gonadal vein (on left side)) between screening and week 9.
- The number and percentage of patients demonstrating an extension of the thrombus into the inferior vena cava between screening and week 9.

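### The at-least-3 success rule counts Mayo reductions in the protocol but also Level 0 renal-vein regression in the SAP, and SAP 4.1 adds an undefined treatment criterion

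*SAP*

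**What the plan says.** The threshold is 3 everywhere, but the counted event changes.

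- Protocol 3.4, under Primary Safety Endpoints: "At least 3 patients showing reductions in Mayo score are required for a positive trial".
- Protocol 9.2: "At least 3 patients showing a reduction in Mayo Classification would produce a positive trial".
- SAP 6: "At least 3 evaluable patients showing improvement in disease extent between screening and week 9 are required for a positive trial". SAP 1.1 and 7.6.1 define improvement. At Level 1 or above it is a Mayo reduction. At Level 0 it is a retreat of the thrombus within or out of the main renal vein. One left-sided case in 7.6.1.2 begins "If the patient is medial to the gonadal vein at screening, a change from the main renal vein medial to the gonadal vein" and ends lateral to that vein.
- SAP 4.1: "at least three evaluable patients should demonstrate an improvement in disease or treatment between screening and week 9", with a reference to 7.6.1.

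The futility rule also differs. Protocol 9.2 says "If no patients have show an improvement in their Mayo classification the trial will be stopped for futility". SAP 3.1.2 stops only if no evaluable patient has improved in disease, and refers to 1.1 and 7.6.1 for the rule and its details.

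Both documents attach the 5% and 25% design rates to improvement in the Mayo classification (protocol 9.1, SAP 4.1). The lowest Mayo category is "Level 0: thrombus limited to the renal vein". Protocol 1.5 deliberately includes patients whose thrombus is confined to that vein.

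**The concern.** With a threshold of 3 in 20, one patient can decide the trial. Two Mayo reductions plus one left-sided medial-to-lateral regression make a positive trial under the SAP and a negative one under protocol 9.2. If that regression is the only response among the first 13 patients, the protocol's futility rule stops the trial and SAP 3.1.2 lets it continue. Because renal-vein thrombus is an intended part of the population, such cases are foreseeable. In an open-label single-arm trial, an unsettled event definition leaves room to choose between verdicts after the results are known.

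The error rates are affected too. The 5% null and 25% target rates were set for Mayo improvement, and the documents give no reason why they carry over to a wider event.

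**Working it through.** **1. The passages side by side.**

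| Patient | Protocol 3.4 / 9.2 | SAP 1.1 | SAP 7.6.1 |
|---|---|---|---|
| Level 1 or above, Mayo level falls | counts | counts | counts |
| Level 0, left, medial to lateral of gonadal vein | does not count (Level 0 before and after) | counts | counts |
| Level 0, left, already lateral, retreats to segmental veins | not stated | does not count | counts |
| Level 0, right, main vein to branches | not stated | counts | counts |
| Level 0, left, lateral and unchanged | does not count | does not count | fits no listed category |

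The last row arises because 7.6.1.2 describes left-sided no change only for a thrombus still medial to the gonadal vein.

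**2. The plan's own design.** Inputs from protocol 9.1 and SAP 4.1: 13 patients in stage 1, 7 in stage 2, continue with at least 1 responder, positive with at least 3 of 20, null rate 5%, target rate 25%, one-sided 10%, power 90%. With X1 ~ Bin(13, p) and X2 ~ Bin(7, p),

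P(positive) = P(X1=1)·P(X2≥2) + P(X1=2)·P(X2≥1) + P(X1≥3).

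- p = 0.05: 0.3512×0.0444 + 0.1109×0.3017 + 0.0245 = 0.0736.
- p = 0.25: 0.1029×0.5551 + 0.2059×0.8665 + 0.6674 = 0.9030.

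Alpha is 7.4% and power 90.3%, so the stated design is reproduced for one event used at both stages. A search over two-stage designs also returns 13 + 7 with these cut-offs as the minimax choice.

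**3. One disputed patient.** The exact p-value for x/20 is P(X1≥1 and X1+X2≥x) at p = 0.05. The 80% limits invert the same distribution with 10% in each tail. The 2/20 row assumes that at least one remaining responder was in stage 1.

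| Result | p-value | 80% interval | Excludes 5%? |
|---|---|---|---|
| 3/20 | 0.074 | 5.7% to 30.5% | yes |
| 2/20 | 0.241 | 2.9% to 24.8% | no |

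**4. Null rate of the wider event.** P(positive) equals 0.10 at p = 0.0570. For assumed null rates of 6%, 7.5% and 10%, alpha is 11.2%, 18.2% and 31.7%. The documents give no null rate for the wider event.

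**5. Upper-end illustration of disagreement.** The documents do not give the inputs. Assume that 25% of patients improve at every level, that a share f of patients is Level 0, and that no Level 0 response counts under the Mayo wording. The Mayo-only rate is then 0.25(1−f). A Mayo-only positive is always an SAP positive, so final disagreement is 0.9030 minus Mayo-only power. Stage-1 disagreement is (1−0.25(1−f))^13 − 0.75^13.

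| f | Mayo-only rate | Mayo-only power | Final verdicts differ | Stage-1 decisions differ |
|---|---|---|---|---|
| 10% | 22.5% | 85.4% | 4.9% | 1.3% |
| 20% | 20.0% | 78.6% | 11.7% | 3.1% |
| 30% | 17.5% | 69.7% | 20.6% | 5.8% |

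These are upper-end figures because they treat every Level 0 response as disputed.

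**The case against.** The best defence is that the SAP settles its own meaning. Section 7 opens with "This section is the complete operational specification for the statistical analysis", SAP 4.1 and 3.1.2 both refer to 7.6.1, and SAP 3.2 already plans 80% intervals for the efficacy proportions. Most of this stands.

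- A reader might infer that the SAP holds two competing futility rules, since 4.1 words stage 1 in terms of Mayo. It does not: 4.1 cites 3.1.2, which leads to 1.1 and 7.6.1. The Mayo wording in 3.1 governs only whether recruitment pauses for the interim analysis. That in section 8 is loose beside SAP 3.2. These are texts to conform, not separate rules.
- A reader might infer that a less invasive operation counts towards the 3, because 1.1 refers to the surgical approach scale and 6.1 links it to improvement. The documents do not support that: surgical approach is a secondary endpoint, 6.1 serves both kinds of endpoint, and no rule says how it would count. The words in 4.1 are undefined; they are not a second route to success.
- A reader might infer that every Level 0 response is lost under the protocol. The protocol does not say how regression right out of the renal vein is scored, and section 1.5 names regression back into the kidney as a hoped-for benefit.

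The defence does not remove the conflict between protocol and SAP on success and futility, the treatment words in 4.1, or the left-sided difference between 1.1 and 7.6.1.2. SAP 6 does not itself cite 7.6.1; reading them together is an inference, though a natural one.

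**Conclusion.** The point holds, and it should be fixed before the primary result is read. The success rule counts different events in the two documents, and one left-sided Level 0 patient is enough to turn 3/20 into 2/20 and reverse both the verdict and the interval's exclusion of 5%. That result follows from the documents' own figures.

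How often it would happen cannot be derived from them. The 4.9%, 11.7% and 20.6% rates rest on assumed Level 0 shares and an assumed 25% response, and lie at the upper end. They should not be read as estimates.

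Nor do the documents show that the design or its alpha is wrong. For one event with rates of 5% and 25%, the design does what it states. What is missing is a single named event, and a reason why those rates apply to it.

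**What to change.** 1. Delete the words *or treatment* from SAP 4.1.
2. Use the SAP 7.6.1 definition of improvement for the hypotheses, stage-1 rule, success rule and interval (SAP 3.1, 4.1, 6 and 8), and amend the protocol to match.
3. Align the left-sided Level 0 rule in SAP 1.1 with 7.6.1.2. Extend the no-change category in 7.6.1.2 to a left-sided thrombus that is lateral at screening and stays there.
4. Remove the surgical-approach pointer from SAP 1.1, and make clear in 6.1 that this scale serves the secondary endpoint.
5. Give the reason why 5% and 25% apply to the wider event, and state that alpha exceeds 10% if its null rate is above 5.7%. Relabelling the rates is not enough.
6. Report the Mayo-only count against the same threshold of 3 as a sensitivity result. SAP 6 already plans the table of Mayo change that supplies it.

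Keeping Mayo reduction as the primary event and reporting Level 0 regression separately would also remove the conflict. The route above follows the SAP's operational definition.

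The cost is wording only, with no new patients or data. The protocol edits fall in the synopsis and in sections 1.5, 2, 3.4, 5.2.11 (primary radiological endpoint), 9.1 and 9.2. The SAP edits fall in 1.1, 3.1, 4.1, 6, 6.1, 7.6.1 and 8. Success becomes easier to meet than under protocol 9.2, by an amount that depends on the Level 0 share, and the amendment should say so.

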4.2 Intention-to-treat (ITT) Population

The Intention-to-treat (ITT) population includes all patients registered onto the study.

4.3 Evaluable Population

The evaluable population includes all patients in the ITT population who have received at least one dose of the study drug (including any patients who were enrolled in error, received study drug and were subsequently found to be ineligible).

4.4 Safety Population

The safety population includes all patients in the ITT population who have received at least one dose of the study drug (including any patients who were enrolled in error, received study drug and were subsequently found to be ineligible). In this study, this population is equivalent to the evaluable population.

5 Safety Evaluations

The study will use the following safety parameters.

5.1 Adverse events, SAEs and SUSARs

All reported adverse events (including adverse reactions, SAEs and SUSARs) will be presented, with events categorised against the National Cancer Institute Common Terminology Criteria for Adverse Events v4.0.

5.2 Early stopping rules

Patient safety will be ensured by applying the following early stopping rules:

- (1) If a single M0 (staging data: cancer has not spread to other parts of the body) patient progresses to the point where surgery is no longer possible, then recruitment of new patients will be suspended following a review by the data monitoring committee (DMC)
- (2) If a single M0 (staging data: cancer has not spread to other parts of the body) patient becomes a M1 (staging data: cancer has spread to other parts of the body) patient, recruitment of new patients will be suspended following a review by the DMC.
- (3) If in 3 patients the VTT extends (as indicated by an increase in Mayo classification) but patients remain surgically resectable the trial will close. If the VTT has extended the patient will be expedited and operated on as soon as possible.

6 Efficacy evaluations

Note that these evaluations will be made for both the evaluable and ITT populations. This represents a sensitivity analysis that assesses whether results are robust in the ITT population.

This study will use the following efficacy parameters:

- At least 3 evaluable patients showing improvement in disease extent between screening and week 9 are required for a positive trial.
- The change in Mayo classification between screening and week 9 in evaluable patients will be presented with the percentage of patients with an improvement, no change and a deterioration in Mayo classification shown. Percentages will be calculated using both the evaluable population and the ITT population.
- The VTT length measurement will be calculated as the sum of: (1) length of IVC tumour thrombus ABOVE renal vein (measured from ostium of RV+IVC to tip of tumour thrombus); (2) length of IVC tumour thrombus BELOW renal vein (measured from ostium of RV+IVC to tip of tumour thrombus) and (3) length of RV thrombus. Those patients who are identified as “main renal vein” will only have the third value populated. Any values that are missing cannot be assumed to represent 0 and must be clarified either via contact with sites or by manual checking of the paper CRF.

- The percentage of patients who have had a change in the surgical approach will be calculated with the percentage with a less invasive and the percentage with a more invasive approach shown separately. Two pieces of data are relevant here: (1) a change from “Open Surgery” to “Minimally invasive surgery”; and (2) a change from a more invasive open to a less invasive open surgical approach (see [Section 6.1](#) for a definition of surgical approach in this respect). Percentages will be calculated using both the evaluable population and the ITT population.
- The response rate, as determined by RECIST criteria v1.1 and provided by sites will be presented and the percentage of outcomes categorised as complete response, partial response and progressive disease shown; only pre-surgical timepoints (i.e., weeks 3 and 9) will be considered. To provide further quality assurance that these RECIST evaluations are correct, the RECIST response will be recalculated from source data by the study statistician and compared to the evaluations provided by sites. Should the evaluations not correspond with each other, a data query will be raised with the sites.
- Morbidity, in terms of the Clavien-Dindo classification system will be presented and percentage of patients with complications of grade I to V will be presented. Percentages will be calculated using both the evaluable population and the ITT population.

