**Secondary outcomes:**

- % change in surgical approach
- % change in VTT height
- Response rate (RECIST)
- Evaluation of surgical morbidity assessed by Clavien-Dindo classification

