1.2 Secondary endpoints

Secondary endpoints are:

- % change in surgical approach
- % change in VTT length
- Response rate (RECIST)
- Evaluation of surgical morbidity assessed by Clavian-Dindo classification

2 Study design

NAXIVA is a single arm, single agent, open label, phase II feasibility study of axitinib in patients with both metastatic and non-metastatic renal cell carcinoma of clear cell histology. 20 evaluable patients will be recruited from multiple centres within the United Kingdom.

Patients who have signed informed consent and who have met all eligibility criteria will be registered into the trial.

The starting dose of axitinib will be 5mg BID, escalated to 7mg BID and then 10mg BID. A dose modification assessment will take place every 2 weeks in clinic during the 8 week pre-surgical treatment period and will be dependent on tolerability of treatment. Patients will follow an aggressive axitinib dose escalation process

within the 8 week period to a maximum of 10mg BID. Patients should stop axitinib a minimum of 36 hours and a maximum of 7 days prior to surgery in week 9.

Blood, urine and tissue samples will be taken prior to and during therapy to evaluate biomarkers of treatment response. Nephrectomy and IVC tumour thrombectomy will be planned for all patients on the trial.

Where there is diagnostic doubt at site, a central review of week 0, 3 and 9 MRI and CT scans will be conducted to determine if a patient has progressed as per RECIST 1.1 criteria. In addition, those particular patient cases will be discussed on an individual basis by the trial steering committee (TSC). In addition, a central review of scans will be carried out once all scans have been carried out to ensure that all measurements are compliant with the NAXIVA MRI SOP (v2.1).

Patients will be assessed at weeks 1, 3, 5, 7, and 9 before surgery and followed up in clinic at 6 & 12 weeks post-surgery.

3 Reporting outline

This section outlines the planned content of interim, final analyses and, if relevant, additional statistical study reports.

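### Surgical morbidity (Clavien-Dindo) is reported only per treated and per registered patient, so patients who never have the operation dilute the rate

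*SAP*

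**What the plan says.** The endpoint is named in SAP 1.2 as "Evaluation of surgical morbidity assessed by Clavian-Dindo classification" and in protocol section 2 as "Evaluation of surgical morbidity assessed by Clavien-Dindo classification".

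For its reporting, SAP 6 states: "complications of grade I to V will be presented. Percentages will be calculated using both the evaluable population and the ITT population". The two populations are:

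- **ITT (SAP 4.2):** this "population includes all patients registered onto the study".
- **Evaluable (SAP 4.3):** this "includes all patients in the ITT population who have received at least one dose of the study drug".

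SAP 6.1 says efficacy outcomes may be expressed on either population, "meaning that the denominator should change to be either the size of the relevant population". SAP 6 describes the use of both populations as follows: "This represents a sensitivity analysis that assesses whether results are robust in the ITT population". SAP 7 adds that "tabulations consist of counts and percentages per category unless stated otherwise", and SAP 7.6.2 lists a single line for the percentage with grade I to V complications. Protocol 9.2 gives no denominator for this endpoint. No section defines a population of operated patients or says how a patient without surgery is to be classified.

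**The concern.** A surgical complication can be observed only in someone who has had the operation. Counting unoperated patients in the denominator treats them, in effect, as operated on without complication.

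The plan itself foresees treated patients who do not reach surgery. Protocol 1.5 lists, as risks of eight weeks of treatment, that an operable tumour may become inoperable and that toxicity may affect fitness for surgery. Stopping rule 1 concerns M0 patients for whom surgery is no longer possible, and SAP 7.5.1 lists a surgery flag with reasons for no operation. Stopping the drug is not enough to create the problem, because patients who discontinue are still followed up (protocol 5.3).

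The ITT figure has a second source of dilution. Under protocol 5.3, patients who never start drug go to surgery outside the study, are not followed up, and are each replaced. They enlarge the ITT denominator and contribute no surgical outcome.

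The direction matters. For an improvement endpoint such as Mayo level, counting patients with no outcome as non-events is conservative. For complications it is flattering. The trial's rationale is less morbid surgery, yet a patient made inoperable or unfit during treatment would make surgical morbidity look better.

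**Working it through.** **Inputs.** The planned evaluable number is N = 20 (SAP 4.1). The documents give no complication rate, no expected number unoperated and no expected number registered but untreated, so those values below are assumptions.

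The 20 comes from the Simon minimax design for 5% versus 25%. An exact two-stage calculation reproduces it: 13 patients then 7, stop if none improve in stage 1, success at 3 or more. This gives one-sided alpha 0.0736 and power 0.903, against the stated limits of 10% and 90%. It is background only; the point does not depend on it.

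**Formula.** Let p be the per-operation complication rate, m the number of treated patients operated on with outcome recorded, and D the denominator. Then

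reported rate = p × m / D.

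**Evaluable population, D = 20, assumed p = 30%**

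| Not operated on | m / D | Reported |
|---|---|---|
| 0 | 20/20 = 1.00 | 30.0% |
| 1 | 19/20 = 0.95 | 28.5% |
| 2 | 18/20 = 0.90 | 27.0% |

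Each unoperated patient costs a relative 1/20 = 5%. In percentage points that is 0.05 × 10% = 0.5, 0.05 × 30% = 1.5 and 0.05 × 50% = 2.5, at assumed rates of 10%, 30% and 50%.

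**ITT population, assumed p = 30%**

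| Registered | Operated, outcome recorded | m / D | Reported |
|---|---|---|---|
| 21 | 20 | 0.952 | 28.6% |
| 22 | 20 | 0.909 | 27.3% |
| 22 | 18 | 0.818 | 24.5% |

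The first two rows show that the ITT figure falls even when every treated patient is operated on.

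**The same relation in counts.** Fix 6 patients with complications among 20 treated. The evaluable figure is 6/20 = 30.0% whatever the number unoperated. The rate per operated patient is not constant:

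| Not operated on | Per operated patient |
|---|---|
| 1 | 6/19 = 31.6% |
| 2 | 6/18 = 33.3% |
| 3 | 6/17 = 35.3% |
| 4 | 6/16 = 37.5% |
| 5 | 6/15 = 40.0% |

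With 22 registered, the ITT figure is 6/22 = 27.3%.

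**Scale.** An approximate 80% interval at 30% of 20 has half-width 1.28 × √(0.3 × 0.7 / 20) = 0.131, about 13 points. A shift of 1.5 to 3 points is well inside that.

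**The case against.** The strongest case on the other side has four parts.

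1. **The wording varies.** The analysis bullet in SAP 6, SAP 7.6.2 and protocol sections 3.4 and 9.2 all speak of morbidity without the word surgical, so a per-treated percentage fits that text. This is true of the wording, but the objectives in both documents name surgical morbidity, and the analysis text does not redefine the endpoint.
2. **A per-treated rate is a legitimate estimand.** It describes the strategy of axitinib followed by planned surgery. The operated-only rate conditions on reaching surgery, which may select fitter patients. This stands. It is a reason to report both figures with the not-operated count, not a reason to report only the diluted one.
3. **The pieces are already there.** SAP 7.5.1 to 7.5.3 list a surgery flag for each patient, SAP 7.5.1 also lists reasons for no surgery, and SAP 7 requires counts as well as percentages. A diligent reader could work out the operated-patient rate. Those listings serve the stopping rules, however, and no planned row separates operated without complication from not operated.
4. **The effect is small.** This is a descriptive secondary endpoint in a single-arm feasibility study, and no decision threshold uses it. This stands and limits the weight of the point.

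SAP 8.1 might be thought to cover the gap. It says only that multiple imputation will be considered above 10% missing, and it does not say whether absence of surgery counts as missing.

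**Conclusion.** The concern holds. Under the stated rule, the only percentages for a surgical outcome use denominators that include patients without surgery. The distortion is zero or downward, never upward. It is zero in the evaluable figure if all treated patients have surgery with outcome recorded, and zero in both figures if no complications occur. Otherwise it is a relative 5% per unoperated patient at N = 20, with a further loss in the ITT figure for each untreated registrant. The actual size cannot be known from the documents, because the number unoperated and the complication rate are both assumed here.

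The ITT version cannot act as a sensitivity analysis for this endpoint, because it only adds patients whose surgical outcome is not recorded. SAP 3.2 sends conflicting evaluable and ITT findings to the DMC; here any difference would come from the denominator alone. The Simon design and the primary endpoint are untouched. This is a change that should be made because it is cheap and corrects a one-directional error, not because it threatens the trial's conclusion.

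**What to change.** In SAP 6 and SAP 7.6.2:

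- Report Clavien-Dindo by grade, with a no-complication row, among treated patients who had nephrectomy and thrombectomy with outcome recorded. Make this the main surgical morbidity figure.
- Show beside it the number treated but not operated on, with reasons.
- Keep the percentage of the evaluable population as a supplementary description of the treatment strategy.
- State that the ITT percentage is not used as a sensitivity analysis for this endpoint.

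The cost is a few lines of SAP text and two table rows. No new data are needed, since the surgery flag and reasons are already planned for the SAP 7.5.1 listing. The downsides are a slightly less favourable headline figure and a rate that conditions on reaching surgery, which is why the not-operated count has to appear in the same table.
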